RPED can occur during treatment with trametinib. In the METRIC trial, where ophthalmologic examinations including retinal evaluation were performed pretreatment and at regular intervals during treatment, one patient (0.5%) receiving trametinib developed RPED and no cases of RPED were identified in chemotherapy-treated patients. Across all clinical trials of trametinib, the incidence of RPED was 0.8% (14/1749). Retinal detachments were often bilateral and multifocal, occurring in the macular region of the retina. RPED led to reduction in visual acuity that resolved after a median of 11.5 days (range: 3 to 71 days) following the interruption of dosing with trametinib, although Ocular Coherence Tomography (OCT) abnormalities persisted beyond a month in at least several cases. Perform ophthalmological evaluation at any time a patient reports visual disturbances and compare to baseline, if available. Withhold trametinib if RPED is diagnosed. If resolution of the RPED is documented on repeat ophthalmological evaluation within 3 weeks, resume trametinib at a reduced dose.

Retinal Vein Occlusion (RVO)

Across all clinical trials of trametinib, the incidence of RVO was 0.2% (4/1749). An RVO may lead to macular edema, decreased visual function, neovascularization, and glaucoma. Urgently (within 24 hours) perform ophthalmological evaluation for patient-reported loss of vision or other

visual disturbances. Permanently discontinue trametinib in patients with documented retinal vein occlusion.

Interstitial Lung Disease

In clinical trials of trametinib at the recommended dose (N = 329), interstitial lung disease (ILD) or pneumonitis occurred in 1.8% of patients. In Trial 1, 2.4% (5/211) of patients treated with trametinib developed ILD or pneumonitis; all five patients required hospitalization. The median time to first presentation of ILD or pneumonitis was 160 days (range: 60 to 172 days). Withhold trametinib in patients presenting with new or progressive pulmonary symptoms and findings including cough, dyspnea, hypoxia, pleural effusion, or infiltrates, pending clinical investigations. Permanently discontinue trametinib for patients diagnosed with treatment related ILD or pneumonitis.

Serious Skin Toxicity

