1.2.6.2 Toxicity

Ocular:

Irreversible retinal damage has been observed in some patients who had received HCQ sulfate. Significant risk factors for retinal damage include daily doses of HCQ sulfate greater than 6.5 mg/kg (5 mg/kg base) of actual body weight, durations of use greater than five years, subnormal glomerular filtration, use of some concomitant drug products such as tamoxifen citrate and concurrent macular disease. A baseline ocular examination is recommended within the first year of starting HCQ. The baseline exam should include best corrected distance visual acuity (BCVA), an automated threshold visual field (VF) of the central 10 degrees (with retesting if an abnormality is noted), and spectral domain ocular coherence tomography (SD-OCT). For individuals with significant risk factors (daily dose of HCQ sulfate greater than 5.0 mg/kg base of actual body weight, subnormal glomerular filtration use of tamoxifen citrate or concurrent macular disease) monitoring should include annual examinations which include BCVA, VF and SD-OCT.

For individuals without significant risk factors, annual exams can usually be deferred until five years of treatment. In individuals of Asian descent, retinal toxicity may first be noticed outside the macula. In patients of Asian descent, it is recommended that visual field testing be performed in the central 24 degrees instead of the central 10 degrees. It is recommended that HCQ be discontinued if ocular toxicity is suspected and the patient should be closely observed given that retinal changes (and visual disturbances) may progress even after cessation of therapy.

Cardiac Effects, including Cardiomyopathy and QT prolongation:

Abbreviated Title: Trametinib and HCQ in BTC

Version Date: 04/06/2022

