3.3.1 Dose reduction

Following dosing interruption due to treatment related toxicity, the offending agent may need to be resumed at a reduced dose as per the dose modification recommendations as following. Dose

reduction should proceed by decreasing the administered dose by 0.5 mg of original dose of trametinib or 400 mg of original dose of HCQ.

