3.3.2 Hydroxychloroquine

Table 4 Guidelines for hydroxychloroquine-related toxicities

Adverse Event	1 st Occurrence	2 nd Occurrence
Hematology Grade 4 neutropenia lasting \geq 7 consecutive days Grade 4 thrombocytopenia \geq 7 consecutive days Grade \geq 3 neutropenia with fever (temperature \geq 38.5 °C)	Hold HCQ and trametinib. Continue weekly hematologic monitoring. Once AE resolves to \leq Grade 1, restart study drugs, with HCQ at next lower dose level.	Discontinue HCQ and trametinib
Skin and subcutaneous tissue disorders Grade \geq 3 rash, hand-foot skin reaction or photosensitivity lasting $>$ 7 consecutive days despite skin toxicity treatment	See Table 5	Discontinue HCQ and trametinib
Eye disorders Grade 2 retinal events lasting $>$ 14 consecutive days confirmed by ophthalmologic examination Grade \geq 3 retinal events confirmed by ophthalmologic examination	Hold HCQ and trametinib. Monitor until AE resolves to Grade \leq 1. Patients should be referred for ophthalmologic exam. Restart study drugs, with HCQ at next lower dose level.	Discontinue HCQ and trametinib
Gastrointestinal Grade \geq 3 nausea or vomiting lasting \geq 7 days despite optimal anti-emetic therapy	Hold HCQ and trametinib. Monitor until AE resolves to Grade \leq 1. Restart study drugs, with HCQ at next lower dose level.	Discontinue HCQ and trametinib
Grade \geq 3 diarrhea lasting \geq 7 days despite optimal anti-diarrhea treatment	See Table 6	Discontinue HCQ and trametinib
Hepato-biliary Grade \geq 3 total bilirubin felt to be not related to progression of disease Grade \geq 3 ALT (isolated increases in AST without concomitant increases in ALT will not be considered dose-limiting because of the non-specific nature of AST) Grade 4 alkaline phosphatase lasting \geq 7 consecutive days felt to be not related to progression of disease	Hold HCQ and trametinib. Monitor with weekly CMP until AE resolves to Grade \leq 1. Restart study drugs, with HCQ at next lower dose level.	Discontinue HCQ and trametinib
ECG QT Interval	Hold HCQ and trametinib. Monitor	Discontinue HCQ

Abbreviated Title: Trametinib and HCQ in BTC**Version Date: 04/06/2022**

Adverse Event	1 st Occurrence	2 nd Occurrence
QTcF interval \geq 501 ms on at least two separate ECGs	with ECG until AE resolves to Grade \leq 1. Restart study drugs, with HCQ at next lower dose level.	and trametinib

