3.3.3 Trametinib

Dose reductions for adverse reactions associated with trametinib are presented in **Table 5**

Table 5: Recommended Dose Reductions for Trametinib for Adverse Reactions

Action	Recommended Dose
First Dose Reduction	1.5 mg orally once daily
Second Dose Reduction	1 mg orally once daily
Subsequent Modification	Permanently discontinue if unable to tolerate trametinib 1 mg orally once daily

Dosage modifications for adverse reactions associated with trametinib are presented in **Table 6**.

Table 6 Recommended Dosage Modifications for Trametinib for Adverse Reactions

Severity of Adverse Reaction ^a	Dosage Modification for Trametinib ^b
Venous Thromboembolism	
Uncomplicated deep venous thrombosis (DVT) or pulmonary embolism (PE)	Withhold trametinib for up to 3 weeks. 
• If improved to Grade 0-1, resume trametinib at lower dose.• If not improved, permanently discontinue trametinib.
Life threatening PE	
Cardiomyopathy	Permanently discontinue trametinib.
Asymptomatic, absolute decrease in left ventricular ejection fraction (LVEF) of 10% or greater from baseline and is below institutional lower limit of normal (LLN) from pretreatment value	Withhold trametinib for up to 4 weeks. 
• If improved to normal LVEF value, resume trametinib at lower dose.• If not improved to normal LVEF value, permanently discontinue

Severity of Adverse Reaction^a	Dosage Modification for Trametinib ^b
	trametinib.
Symptomatic cardiomyopathy Absolute decrease in LVEF of greater than 20% from baseline that is below LLN	Permanently discontinue trametinib.
Ocular Toxicities	
Retinal pigment epithelial detachments (RPED)	Withhold trametinib for up to 3 weeks. 
• If improved, resume trametinib at same or lower dose.• If not improved, permanently discontinue trametinib or resume trametinib at lower dose.
Retinal vein occlusion (RVO)	Permanently discontinue trametinib.
Pulmonary	
Interstitial lung disease (ILD)/pneumonitis	Permanently discontinue trametinib.
Febrile Reactions	
Fever higher than 104°F Fever complicated by rigors, hypotension, dehydration, or renal failure	Withhold trametinib until fever resolves, then resume trametinib at same or lower dose.
Skin Toxicities	

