3.6.1 Criteria for Removal from Protocol Therapy

- Participant requests to be withdrawn from active therapy
- Unacceptable toxicity (both drugs) as described in Section [3.3](#)
- PI discretion
- Positive pregnancy test or intent to become pregnant
- Drugs become unavailable
- Initiation of therapy that prevents further administration of study treatment
- Confirmed disease progression based on radiographic progression per RECIST 1.1.
- Permanent loss of capacity to consent, per requirements of section [12.3](#)

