4 CONCOMITANT MEDICATIONS/MEASURES

All routine and appropriate supportive care (including blood products) will be provided during this study, as clinically indicated, and in accordance with the standard of care practices. Clinical judgment should be utilized in the treatment of any adverse event experienced by the patient.

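### Table 4 requires no HCQ action for retinal toxicity until well after the point at which section 1.2.6.2 recommends stopping the drug

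*Combined protocol and SAP*

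**What the plan says.** The protocol handles retinal toxicity in three places.

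- **Safety text for HCQ (section 1.2.6.2, Ocular).** "It is recommended that HCQ be discontinued if ocular toxicity is suspected". No grade, duration or confirmation is attached. The reasons given are that retinal damage has been permanent in some patients and can go on worsening after the drug is stopped.
- **Dosing table for HCQ (section 3.3.2, Table 4, eye row).** Action is required for a Grade 2 retinal event lasting more than "14 consecutive days confirmed by ophthalmologic examination", or for a confirmed event of Grade 3 or higher. Both drugs are then held until Grade 1 or lower. The row continues: "Patients should be referred for ophthalmologic exam. Restart study drugs, with HCQ at next lower dose level". Discontinuation comes only at the second occurrence.
- **Trametinib rules (section 1.2.5.2 and section 3.3.3, Table 6).** For retinal pigment epithelial detachment (RPED), section 1.2.5.2 says "If resolution of the RPED is documented on repeat ophthalmological evaluation within 3 weeks, resume trametinib at a reduced dose". Table 6 says "If improved, resume trametinib at same or lower dose", and without improvement it allows either permanent discontinuation or a lower dose. For retinal vein occlusion (RVO), both places stop trametinib permanently.

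Section 3.3 is the set of rules that sites are sent to. Under section 3.3.1, "the offending agent may need to be resumed at a reduced dose as per the dose modification recommendations". Section 3.6.1 removes patients from therapy for "Unacceptable toxicity (both drugs) as described in Section" 3.3.

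**The concern.** A site that follows Table 4 to the letter acts later than section 1.2.6.2 recommends, because it waits for duration and confirmation instead of acting on suspicion. It also acts more weakly, because it restarts HCQ where the safety text discontinues it. The row asks for ophthalmologic confirmation before anything happens, yet lists the ophthalmology referral among the actions that follow.

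At stake is avoidable HCQ exposure in a patient whose retina may already be affected, where the protocol itself says that stopping may not halt the damage.

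A smaller problem sits in the same row. It tells sites to restart the study drugs after a retinal event, names a lower level only for HCQ, and makes no exception for RVO.

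**Working it through.** No design figure is involved, so the check is a comparison of the texts plus some side arithmetic.

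**1. HCQ rules side by side**

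| | Section 1.2.6.2 | Table 4, eye row |
|---|---|---|
| Trigger | Suspicion | Confirmed Grade 2 for more than 14 days, or confirmed Grade 3 or higher |
| First action | Discontinue HCQ | Hold both drugs until Grade 1 or lower |
| Re-treatment | None described | HCQ one level lower; discontinue at second occurrence |

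**2. Exposure before Table 4 requires action (Grade 2 event)**

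The dose is 600 mg twice daily, or 1,200 mg/day (section 3.1). More than 14 days means at least 15 days: 15 × 1,200 = 18,000 mg.

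**3. Dose against the protocol's own risk threshold**

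Section 1.2.6.2 names more than 6.5 mg/kg/day as a significant risk factor.

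- Full dose: 1,200 / 6.5 = 184.6 kg, so every patient below that weight exceeds it.
- After one 400 mg reduction (section 3.3.1): 800 / 6.5 = 123.1 kg.
- Body weight is not given. Over an assumed 50 to 100 kg, the full dose is 24.0 to 12.0 mg/kg and the reduced dose 16.0 to 8.0 mg/kg.

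Table 4's restart dose would therefore leave all patients in that weight range above the threshold.

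**4. How often the eye is examined**

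Scheduled examinations are at screening, C2D1 and every 3 cycles thereafter (section 3.4, footnote 5). After C2D1 they are 3 × 28 = 84 days apart, with others as clinically indicated. Suspicion can therefore arise between scheduled visits.

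**5. Trametinib events that could meet Table 4's eye row**

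These are the all-trial rates in section 1.2.5.2, applied to the 17 patients of the full two-stage cohort.

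- RPED: 14/1749 = 0.80%; 17 × 0.0080 = 0.14 expected; 1 − (1 − 0.0080)^17 = 13% chance of at least one.
- RVO: 4/1749 = 0.23%; 17 × 0.0023 = 0.04 expected; 1 − (1 − 0.0023)^17 = 4% chance of at least one.

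**6. Dose cost of an early HCQ hold**

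HCQ doses per cycle: 28 × 2 = 56.

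- 5 days: 10/56 = 17.9% missed, 82.1% taken.
- 6 days: 12/56 = 21.4% missed, 78.6% taken.

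A hold of up to 5 days stays within the 20% missed-dose allowance (section 3.2.2) and the 80% rule for DLT evaluability (section 3.1.2). A 6-day hold does not.

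**The case against.** The strongest reply is that the two HCQ texts are not incompatible. Section 1.2.6.2 is background in the form of a recommendation, and Table 4 is itself headed as guidelines. Earlier stopping is open to the investigator through PI discretion (section 3.6.1) and section 4: "Clinical judgment should be utilized in the treatment of any adverse event experienced by the patient". Scheduled eye examinations fall on Day 1 of a cycle, where section 3.3 has both drugs held together. An RPED found then would normally interrupt HCQ as well, since Table 6 withholds trametinib for any RPED. Table 4's trigger also closely follows the retinal criteria for dose-limiting toxicity in section 3.1.1, so it may be a deliberate threshold.

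Most of this stands, and it limits the point. A reader might infer that Table 4 bars stopping on suspicion; it does not. What remains is that discretion permits the earlier hold without requiring it. The joint hold does not cover findings between cycle starts, and it lets the PI leave the other drug unchanged when one drug alone is blamed.

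Four other strong readings are tempting, and the documents do not support them:

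- **That the RVO rules contradict each other.** Section 1.2.5.2 and Table 6 agree. A conflict arises only if an RVO is handled under Table 4's generic row, and that table is for HCQ-related events. Patients with a history of RVO or current risk factors are also excluded (section 2.1.2), so 0.04 expected cases may be too high.
- **That one RPED rule is wrong.** The texts differ, but section 1.2.5.2 is silent on non-resolution. Resuming at a reduced dose after resolution within 3 weeks satisfies both. Nothing in the documents shows which rule is right.
- **That the lack of an HCQ row for a fall in LVEF below Grade 3 is an error.** It is a gap, partly covered by the joint hold at cycle start and by Table 4's row for non-hematologic events of Grade 3 or higher.
- **That the mg/kg figures predict many retinal events.** Section 1.2.6.2 also lists more than five years of use as a risk factor, and no short-term rate is given.

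**Conclusion.** The point holds for HCQ and the retina. Exact compliance with Table 4 is less protective than the protocol's own safety text, for a harm that the protocol describes as sometimes irreversible. This is worth correcting at the next amendment.

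Few patients are likely to be affected. No expected count can be given for HCQ retinal toxicity, because the documents contain no rate for this treatment duration. The RPED and RVO figures (0.14 and 0.04 of 17) assume that trametinib rates from other trials carry over to this combination and population.

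The missing RVO exception in Table 4 is a small drafting matter. The RPED difference is minor and needs alignment by the sponsor. The primary endpoint, alpha, power and sample size are not touched.

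**What to change.** 1. **Table 4, eye row, HCQ.** Hold HCQ as soon as retinal toxicity is suspected, pending ophthalmologic examination. Discontinue it if HCQ retinal toxicity is confirmed or not excluded.
2. **Table 4, eye row, trametinib.** Add that any trametinib restart after RPED or RVO follows Table 6, so that RVO means permanent discontinuation of trametinib.
3. **RPED.** The sponsor should choose one resume rule and state it identically in section 1.2.5.2 and Table 6.
4. **Run-in.** State in section 3.1.1 whether an HCQ stop for retinal toxicity counts as a DLT. Otherwise a patient who stops early could fall below 80% of doses without meeting the more-than-14-day criterion, and section 3.1.2 would replace that patient. Counting the stop as a DLT avoids this and makes the rule of fewer than 2 DLTs in 6 patients slightly stricter.

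Simply declaring that section 3.3 prevails would not help, because it would fix the less protective rule in place.

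The cost is a wording amendment and a few more HCQ interruptions; where the joint hold applies, trametinib doses are lost too. Holds of 6 days or more exceed the 20% allowance, so the amendment should say that a hold under this row is not a compliance breach. No new procedure is needed. Eye examinations are already scheduled or allowed as clinically indicated, and section 1.2.5.2 already asks for one within 24 hours of a reported visual disturbance.

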1.2.6.3 Toxicities of the combination of trametinib and HCQ

There is no data available in terms of this combination though there should have this information accessible in the near future since several trials involved with this combination is ongoing. However, there is safety data from the BAMM trial (NCT02257424), that is designed for patients with advanced BRAF mutant melanoma treated with dabrafenib, trametinib, and hydroxychloroquine. The doses of trametinib and hydroxychloroquine used in the BAMM trial is the exact same as we plan in our trial except that we are not planning BRAF inhibitor dabrafenib. Therefore, this precious data will provide important reference for our trial. From personal communication with [name] (Primary Investigator of BAMM trial, University of Pennsylvania), we summarize the safety profile from BAMM trial as showed in the following **Table 3**.

Table 3. Safety profile in the BAMM Study

Adverse Event	Dabrafenib + trametinib + HCQ (BAMM)	
	Grade 1-2	Grade 3
Chills	14 (56%)	1 (4%)
Diarrhea	13 (52%)	0
Fever	13 (52%)	1 (4%)
Nausea	12 (48%)	1 (4%)
Fatigue	11 (44%)	0
Headache	9 (36%)	0
Myalgia	9 (36%)	0
Rash	9 (36%)	3 (12%)
Anorexia	8 (32%)	0
Dry mouth	7 (28%)	0
Pruritus	7 (28%)	0
Arthralgia	6 (24%)	0
Abdominal pain	5 (20%)	0
Vomiting	5 (20%)	0
Constipation	4 (16%)	0
Dysgeusia	4 (16%)	0
Creatinine increased	3 (12%)	0
Dehydration	3 (12%)	2 (8%)
QTc prolonged	3 (12%)	1 (4%)
Increased alanine aminotransferase	1 (4%)	2 (8%)
Ejection fraction decreased	0	1 (4%)

With the triplet combination, the most common adverse effects are chills, diarrhea, fever, nausea, rash, and fatigue with grade 1-2. No grade 4 AEs are reported. This information indicates the less adverse effects we foresee with trametinib and hydroxychloroquine in our trial.

1.2.7 Drug dose rationale

Given there is a previously described efficacious dosing for trametinib at 2 mg once daily for metastatic melanoma with described de-escalation for trametinib associated side-effects, we will keep this dosing static and only de-escalate if trametinib specific, dose limiting side effects are encountered. As we do not know the dosing of HCQ needed to inhibit trametinib-induced autophagy, we will use flat dose as 600 mg twice daily used in previous mentioned PDAC trial and de-escalate if HCQ specific, dose limiting side effects are encountered. Both drugs are orally bioavailable and will be dosed orally. Drug-drug interactions between trametinib and HCQ are not expected due to separate metabolism and transporter pathways.

2 ELIGIBILITY ASSESSMENT AND ENROLLMENT

2.1 Eligibility Criteria

2.1.1 Inclusion Criteria

- Histopathological confirmation of:
 - biliary tract carcinoma (BTC)

OR

- carcinoma in the setting of clinical and radiological characteristics which, together with the pathology, are highly suggestive of a diagnosis of BTC

Note: The term BTC includes intra- or extra- hepatic cholangiocarcinoma (CCA), gallbladder cancer or ampullary cancer.

- The tumor must have KRAS mutation(s) of clinical significance, confirmed by NCI Laboratory of Pathology or by FDA approved test.
- Patients must have received or been intolerant of at least one line of chemotherapy.
- Patients must have at least 1 measurable lesion by RECIST version 1.1 (see section **6.3**)
- Patients must have disease that is not amenable to potentially curative resection, ablation or transplantation.
- Age \geq 18 years.
- Performance status (ECOG) 0-2 (see [Appendix A](#))
- If liver cirrhosis is present, patient must have a Child-Pugh score <7 (Class A) (Section [Appendix B](#))
- Patients must have adequate organ and marrow function as defined below:

ANC	$\geq 1,500/\text{mcL}$
platelets	$\geq 100,000/\text{mcL}$
hemoglobin	$\geq 9 \text{ g/dL}$
total bilirubin	If cirrhosis present: Part of Child Pugh requirement If no cirrhosis: bilirubin should be $\leq 1.5 \times \text{ULN}$
ALT or AST	$\leq 5 \times \text{ULN}$.
Creatinine OR Measured or calculated creatinine clearance (CrCl) (eGFR may also be used in place of CrCl) ^A	$< 1.5 \times$ institution upper limit of normal OR $\geq 30 \text{ mL/min}/1.73 \text{ m}^2$ for participant with creatinine levels $\geq 1.5 \times$ institutional ULN
ALT (SGPT)=alanine aminotransferase (serum glutamic pyruvic transaminase); AST (SGOT)=aspartate aminotransferase (serum glutamic oxaloacetic transaminase); GFR=glomerular filtration rate; ULN=upper limit of normal.	
^A Creatinine clearance (CrCl) or eGFR should be calculated per institutional standard.	

- Patients must have at least 1 focus of disease that is amenable to mandatory tumor biopsies and be willing to undergo this. Ideally, the biopsied lesion should not be one of the target measurable lesions, although this can be up to the discretion of the investigators.
- The study drugs are harmful for developing human fetus. For this reason, women of child-bearing potential and men must agree to use adequate contraception (hormonal or barrier

method of birth control; abstinence) at the study entry, for the duration of study treatment and up to 4 months after the last dose of the study drug(s). Should a woman become pregnant or suspect she is pregnant while she or her partner is participating in this study, she should inform her treating physician immediately.

- Patients must be able to understand and be willing to sign a written informed consent.

